6.0 Number of Subjects

Forty-eight patients-participants and up to six raters-participants will be recruited for the study.

7.0 Setting

Data Collection Site: All data collection and study activities will be conducted at the Medical University of South Carolina (MUSC). The patient subject sample will include 48 treatment-seeking patients diagnosed with presbyphonia at the Evelyn Trammell Institute for Voice and Swallowing (division of the Department of Otolaryngology-Head & Neck Surgery). The sample will be limited to the MUSC site because historical accruals have been shown sufficient to meet power (see participant section above). Further, the data quality and logistical challenges faced in multi-site trials go beyond the scope and expense of this current proposal. Participant raters will be recruited from SLPs who have an affiliation with MUSC and who have experience in working with voice patients.

8.0 Recruitment Methods

Following IRB approval, participants will be recruited from the treatment-seeking population at the Evelyn Trammell Institute for Voice and Swallowing (division of the Department of Otolaryngology-Head & Neck Surgery) - Medical University of South Carolina (MUSC). As part of usual care, all patients will undergo a videostroboscopic assessment conducted by the laryngologist, [name] and will be referred to voice

therapy with a certified SLP to start usual treatment. Patients will undergo a brief screening interview by [name], after which qualifying patients will be offered participation in the study.

9.0 Consent Process

Interested and eligible patients will meet with a study team member shortly after being informed of the study (on the same day if possible). The consent process will take place in Rutledge Tower. The study member will provide a detailed description of the study and of its risks and benefits and the patient will be handed a written document with all the information. The study member will then discuss with the prospective participant and will ask specific questions to ensure a good understanding of key elements related to the study. Patients will be prompted to ask any questions they have. Finally, patients will be informed that their decision to participate or not in the study will not impact the care that they will receive at MUSC. Following this procedure, written consent will be obtained from interested participants. Following muscle pressure testing, participants whose muscle pressure results don't meet stratification requirements will be excluded from the study.

10.0 Study Design / Methods

Overview

After being enrolled in the study, treatment-seeking patients with a diagnosis of presbyphonia will undergo baseline respiratory assessments including spirometry and respiratory muscle strength measures as well as voice recordings (acoustic assessments). Participants will then be blocked-randomized (based on their MIP and MEP) to one of three groups using a 3-parallel arm design: (2 experimental groups and 1 control group), using a 3-parallel arm design: 1) inspiratory training (IMST) (experimental group), 2) expiratory training (EMST) (experimental group), or 3) standard of care (VFE) (control group), delivered four times (see table 1 for participant timeline). The sessions will occur on the same days as the participants' scheduled voice therapy sessions when possible. Participants will be asked to practice their respective exercises for 10 minutes, twice daily, seven days a week during the duration of the study. A final assessment session, after the 4th therapy session, will mirror the baseline measures. Participants will receive a monetary compensation of \$20 for each study visit, for a maximum of \$80 for the whole study. Payments will be made via cash. Outcomes that rely on subjective judgment (visual ratings of

videostroboscopy and perceptual judgments of voice quality) will be rated by trained judges (SLPs) blinded to the group assignment. [**Note**: Long-term follow-up will not be conducted. This study's focus is on the mechanistic effects of the intervention; future studies, given positive outcomes from this study, will explore the effectiveness and long-term effects.]

Table 1: Participant Timeline

Visit 1	Visit 2	Visit 3	Visit 4
Baseline assessment session			
Therapy session 1	Therapy session 2	Therapy session 3	Therapy session 4
			Final assessment session

Patient Participants

Standard of Care Assessments (Procedures being performed already for diagnostic purposes)

- Laryngeal imaging: prior to the examination, the laryngologist will administer topical lidocaine and neosynepherine in a spray to one of the nasal cavities. The laryngologist then passes the camera through the nose to examine the vocal folds. The participant will be asked to sustain phonation on the vowel /i/ for at least 3 seconds and to repeat with pitch and loudness variations.
- Acoustic Assessments: The microphone is positioned at a 45° angle and at a standardized distance from the mouth of the participant. The participant is asked to sustain phonation on the vowel /a/ at a comfortable loudness for 3-5 seconds and as loud as possible for 2 seconds, and to glide to a high pitch and to a low pitch. They are then asked to read the 6 CAPE-V sentences and to have a

short natural conversation with the speech therapist. The participant is then asked to rate their perceived phonatory effort (PPE) on a scale.

- Self-assessments: The participant is asked to fill out the Voice Handicap Index questionnaire, the Reflux Symptom Index, and the Glottal Function Index.
- Aerodynamic assessments: The participant wears a face mask over the nose and mouth, which directs the air flow. A tube connected to a pressure transducer is passed through a hole in the mask, and inserted between the lips. The participant is asked to produce short utterances each comprised of minimally five /pi/ syllables at a rate approximating 1.5 2 syllables per second (/pi-pi-pi-pi-pi/). Each string of at least five syllables should be produced on one breath/exhalation. The task is repeated 3 times at comfortable pitch and loudness.

Standard of Care Intervention (Procedures being performed already for treatment purposes)

- Vocal Function Exercises: Participants in all 3 groups will be instructed to follow the 4 steps of the Vocal Function Exercises (VFE) protocol, developed by Stemple (2005) and commonly used by speech language pathologists (SLP) with voice patients: (a) sustain the vowel /i/ on the musical note F (above middle C for women; below middle C for men) for as long as possible. Repeat as judged by the SLP. (b) Glide from the lowest note to the highest note on the word "knoll". Repeat as judged by the SLP. (c) Glide from the highest note to the lowest note of the word "knoll". Repeat as judged by the SLP. (d) Sustain the notes C-D-E-F-G (starting from middle C for women and an octave below middle C for men) on the word "oll", for as long as possible. Each note will be repeated until the participant finds the right placement (forward-focused voice), as judged by the SLP. Humming exercises will be used to facilitate placement of the voice.
- Counseling and patient education during the therapy sessions.

Experimental Assessments (Procedures to be performed solely as part of this research study):

Firstly, the medical chart of the participant will be reviewed to obtain the following information: height and weight. This information will be used to perform the respiratory and muscle pressure assessments. The medical chart will also be used to track the speech therapy appointments, since research visits will take place on the same days. Spirometry assessments will take place at baseline and after the fourth intervention session. Muscle pressure testing and acoustic assessments will be conducted at baseline and before and after each intervention session.

Spirometry: Prior to the tasks, the participant will put on a nose clip and make sure that the lips are well sealed around the tube with no air is escaping. They will be asked to breathe normally, and then take a full inspiration and blow out with force during at least 6 seconds, in the spirometer. Those maneuvers will be repeated at least three times, to verify test reliability. No more than eight repetitions should be needed(47). The participant is seated to reduce risks of fall.

• Muscle pressure (maximum inspiratory pressure-MIP- and maximum expiratory pressure-MEP):

- o MIP: the participant is instructed to exhale slowly and completely, seal lips firmly around the mouthpiece, and then breathe in forcefully. The PI will note the largest negative pressure sustained for at least one second on the pressure gauge. The participant will rest for about one minute and then repeat the maneuver up to 4 additional times (with the goal of matching the highest 2 trials within 10 cmH₂O)(48).
- o MEP: the participant is instructed to inhale slowly and completely, seal lips firmly around the mouthpiece, and then breathe out forcefully. The PI will note the largest positive pressure sustained for at least one second on the pressure gauge. The participant will rest for about one minute and then repeat the maneuver up to 4 additional times (with the goal of matching the highest 2 trials within 10 cmH₂O) (48).
- Acoustic assessment: The microphone is positioned at a 45° angle and at a standardized distance from the mouth of the participant. The participant is asked to sustain phonation on the vowels /a/ and /i/ at a comfortable loudness for 3-5 seconds and as low and as loud as possible, to glide to a high pitch and to a low pitch, and from a soft voice to a loud voice. They are asked to sustain the vowel /a/ for as long as possible. They are then asked to read the 6 CAPE-V sentences and to have a short natural conversation with the speech therapist. The participant is then asked to rate their perceived phonatory effort (PPE) on a scale.
- Self-Assessment questionnaire: the participant will be asked to fill out the Communicative
 Participation Item bank (CPIB) questionnaire, which consists of 10 questions on communication.

Participants will be stratified based on their muscle pressure measures: 1) within normal limits MIP and MEP; 2) preserved MIP and decreased MIP; 3) preserved MEP and decreased MIP; 4) decreased MIP and MEP. This stratification is crucial to the study design because it will ensure an equal repartition of the

different respiratory profiles and deficits across treatment groups. Participants that don't meet stratification requirements will be excluded from the study.

Participants will be blocked-randomized into three groups (allocation ratio 1:1:1): IMST, EMST and VFE (see description of the interventions below).

Experimental Interventions (Procedures to be performed solely as part of this research study):

Participants in all groups will attend four sessions with a study team member. Intervention sessions will last approximately 30-45 minutes each. Each session will include pre- and post-treatment muscle pressure and acoustic measurements.

- Inspiratory Training: Inspiratory training will be conducted using an inspiratory pressure threshold trainer (Philips Respironics® Threshold IMT or POWERbreathe® Medic Plus, for patients with a MIP more than 83 cmH₂0), which consists of a mouthpiece with a spring-loaded valve(25). The valve blocks the airflow until the threshold pressure achieved and allows airflow as long as the sufficient pressure is maintained. The threshold will be set at 75% of the participant's initial MIP, as reported in the literature with elderly participants(16). If it is too hard for the participant, the load will be lowered until the participant is able to perform the exercises. The load will be adjusted weekly by the study team member to maintain a threshold at 75% of the participant's MIP. Daily practices will consist of 5 sets of 5 breaths with the device with a break between sets, repeated twice daily (15, 18, 31).
- **Expiratory Training**: Expiratory training will be conducted using an expiratory pressure threshold trainer (EMST150) which consists of a mouthpiece with a spring-loaded valve. The valve blocks the airflow until the threshold pressure is produced (set at 75% of the participant's initial MEP, per literature with similar age groups(32-34)), and allows the airflow as long as the sufficient pressure is maintained. Participants will be asked to exhale forcefully into the mouthpiece after a full inspiration. If it is too hard for the participant, the load will be lowered until the participant is able to perform the exercises. The load will be adjusted weekly by the study team member to maintain a threshold at 75% of the participant's MEP. Daily practices will consist of 5 sets of 5 breaths with the device with a break between sets, twice daily(32-34).

Home Practice: Participants will be instructed to practice their respective exercises twice daily, and to log their practice in a compliance journal (days of training, perceived effects of treatment or other comments)

as well as to contact a research team member if any difficulty arise. In addition to in-person therapy sessions, weekly phone calls will clarify aspects of the training and encourage treatment adherence.

Rater Participants

Procedures that will be performed solely as part of this research study:

Raters will rate the audio recordings with the CAPE-V form and the videostroboscopy images with the VALI form. They will rate pre- and post-intervention de-identified recordings for each participant, and an additional sampling of 20% of the recordings (for intrarater reliability testing).

Data Collection

Data collected will be the same for Aim 1 and Aim 2. It will include information in the patient's medical record (obtained from standard of care assessment) and obtained through a demographic questionnaire as well as clinical data using standardized collection instruments: spirometry measures, muscle pressure measures and acoustic assessment.

Each video and audio recording will be de-identified when videos are converted into .mpg, .nsp or .mp3 files before distributing the recordings via Box for analysis. Participant raters will review the de-identified digitized recordings for the purposes of data collection and score each video and audio recording using the VALI and CAPE-V rating forms, respectively.

Spirometry, muscle pressure data, and voice data will be recorded in a data collection sheet by the study team member. Data collection sheets will be labeled with the alphanumeric identifier of the patient-participant. Completed data collection sheets, with ratings from the CAPE-V and VALI, will be entered in the database by a study team member. Research records will be retained for a period of six years to allow evaluation and repetition of the results by others.

Study personnel will enter mandatory data fields for demographics according to the NIH minimum standards for maintaining, collecting and presenting data on gender, race and ethnicity. The demographic and clinical data will be exported for analysis.

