The effects of respiratory training on voice outcomes have never been studied on patients with presbyphonia despite the declines in respiratory function that occur with aging. Both inspiratory and expiratory pressures can be reduced in elderly patients, yielding different impairment profiles (10). Since inspiratory muscles are crucial for increasing inspiratory lung volume and for counteracting expiratory pressures to enhance airflow control during sustained speech, increasing their strength appears to be a viable target to improve the loudness and duration of speech (29). However, some individuals may have difficulty generating sufficient subglottal pressure despite initiating phonation at high lung volume because of reduced ribcage compliance and lung recoil forces(11, 12). For those patients, early activation of the expiratory muscles might be the most effective strategy to increase vocal efficiency, by compressing the chest wall to a smaller volume and generating the required airway pressure for speech production (19, 30). These patients may optimally benefit from expiratory training. Although some patients may benefit from both inspiratory and expiratory training, there is a need to assess the individual effects of both interventions prior to testing their combined effect in a future study to understand the mechanism of action and optimize the use of therapy time. Thus, we propose to study how differences in patients' baseline respiratory function impacts intervention response, specifically which patients benefit from inspiratory training and which patients benefit from expiratory training.

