5.0 Inclusion and Exclusion Criteria/ Study Population

Patients who are diagnosed with presbyphonia and who have already sought and begun voice care at MUSC, will undergo a brief screening interview by [name], after which qualifying patients will be offered participation in the study. A study team member will meet with interested participants and will provide a thorough description of the study prior to obtaining formal written consent. Participants who don't meet stratification requirements will be excluded from the study.

Inclusion Criteria

The participant:

- must receive a diagnosis of presbyphonia by a trained laryngologist. The
 diagnosis will be given following a visual examination of the larynx if the
 observations are consistent with the characteristics of a presbylarynx, as
 judged by the laryngologist.
- must have already undertaken their voice care at MUSC
- must be 50 years and older
- must be English-speaking
- must sign the informed consent

Exclusion Criteria

The participant

- has received voice therapy in the past year (other than current care)
- presents with a vocal fold pathology other than presbyphonia
- has a known neurologic or a progressive neuromuscular disease
- doesn't meet the stratification requirements for muscle pressure
- has a medical condition that could be aggravated by the experimental intervention, or any condition judged by the physician ([name]) as being unsuitable for respiratory training.
- has dysarthria or a language disorder
- has a hearing loss that is not adequately managed
- has a cognitive disorder that might affect treatment compliance
- is unable to give informed consent

Inclusion of Women

No subjects will be excluded based on gender. Based on published literature, treatment seeking patients with presbyphonia are generally equally divided between female and male. Thus, we estimate that approximately 50% of study participants will be female. No outreach program to recruit women is planned, because all patients with presbyphonia who meet inclusion criteria after undergoing a voice evaluation at the participating institution, regardless of gender, will be invited to participate. While no subjects will be excluded based on gender, it is highly likely that the majority of participant raters will be women as that is the current composition of speech-language pathologists.

Inclusion of Minorities

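### Stratum 2 of the randomisation list is impossible as printed, the exclusion tied to that list removes the wrong patients or nobody, and Aim 1 leaves out the factors randomised on

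*Combined protocol and SAP*

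**What the plan says.** **Strata.** Section 10.0 (Experimental Assessments) puts normal MIP and MEP in stratum 1 and continues: "2) preserved MIP and decreased MIP; 3) preserved MEP and decreased MIP; 4) decreased MIP and MEP". It gives the list great weight: "This stratification is crucial to the study design because it will ensure an equal repartition" of respiratory profiles between the arms. The overview of the same section confirms that allocation uses these measures: "Participants will then be blocked-randomized (based on their MIP and MEP) to one of three groups".

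**Exclusion.** Three sections tie eligibility to the list. Section 5.0 excludes anyone who does not "meet the stratification requirements for muscle pressure". Section 9.0 places the exclusion after written consent: "Following muscle pressure testing, participants whose muscle pressure results" fall short are removed. Section 10.0 repeats that those who do not "meet stratification requirements will be excluded from the study". None of the three says what the requirements are.

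**Analysis.** The Aim 1 model in section 12.0 (Data Analysis Plan) names time, with two levels, and intervention, with three. MIP and MEP enter only as predictors in the Aim 2 logistic regression.

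**The concern.** One list does two jobs: it defines the randomisation strata and it decides who stays in the trial after testing. An error in it therefore reaches both allocation and eligibility.

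The profile that falls out is preserved MIP with decreased MEP. The Background expects such profiles: "Both inspiratory and expiratory pressures can be reduced in elderly patients, yielding different impairment profiles". Aim 2 Hypothesis 2 (section 1.0) says that expiratory training works best in patients with decreased MEP, so the patients without a stratum are ones that hypothesis needs.

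The analysis is a separate and smaller matter. Stratified randomisation makes the arms more alike than simple randomisation would. A model that ignores the strata still counts the between-stratum variation as noise. The test then rejects less often than its nominal level and gives up power that the design has already paid for.

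**Working it through.** **1. Strata against the possible patients.** Each pressure is either preserved or decreased, which gives four combinations.

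| MIP | MEP | Stratum as printed | Stratum after correction |
|---|---|---|---|
| preserved | preserved | 1 | 1 |
| preserved | decreased | none | 2 |
| decreased | preserved | 3 | 3 |
| decreased | decreased | 4 | 4 |

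As printed, stratum 2 is empty and one combination has no stratum. After correction every combination has exactly one.

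**2. What the exclusion then does.** Applied to the printed list, it removes the second row. Applied to the corrected list, it removes no one with both pressures measured. Under neither reading does it have a sensible stated purpose.

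**3. The plan's own sample size.** Inputs from section 12.0: d = 0.90, alpha 0.10, power 80%, 15 per group, 10% dropout, 48 recruited. By the normal formula, two-sided, n = 2(1.645 + 0.842)²/0.90² = 15.3, or 16 after rounding up; the t-test gives 15.99. The stated 15 is reproduced to within one patient. Nothing below changes it.

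**4. Type I error without the strata, by hand.** Section 1.0 hypothesises greater improvement, so the relevant test compares change between arms. With 15 completers per arm, the residual degrees of freedom are 45 − 3 = 42. For an F statistic with 2 and 42 df, P(F > x) = (1 + 2x/42)^(−21), so the 0.10 critical value is 21(10^(1/21) − 1) = 2.434. Let R² be the share of the variance of change that the strata explain; the documents do not give it. If arms are balanced within strata, differences between arm means shrink by the factor 1 − R² in variance, while the residual does not. The test then behaves roughly like (1 − R²)F, and its true level is P(F > 2.434/(1 − R²)):

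- R² = 0.10: P(F > 2.704) = 0.079
- R² = 0.25: P(F > 3.245) = 0.049
- R² = 0.40: P(F > 4.056) = 0.025

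**5. Simulation.** Settings: 48 patients, four equal strata, permuted blocks of 3 within stratum, 10% random dropout, both training arms shifted equally against voice exercises alone, F-test of arm on change at 0.10. Stratum mix, block size and R² are assumptions. With the shift set at 0.90 SD of change (12,000 runs):

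| R² | Type I, without | Type I, with | Power, without | Power, with |
|---|---|---|---|---|
| 0 | 0.099 | 0.099 | 0.784 | 0.781 |
| 0.10 | 0.076 | 0.097 | 0.779 | 0.814 |
| 0.25 | 0.050 | 0.102 | 0.796 | 0.883 |
| 0.40 | 0.028 | 0.098 | 0.802 | 0.939 |

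A second set of 6,000 runs gave type I error without the strata of 0.086, 0.055 and 0.032, and power gains of 2.7, 8.6 and 12.7 points. Together the gains are about 3, 9 and 13 points. Unequal strata (assumed 55/15/15/15%) gave nearly the same: 0.090, 0.055 and 0.032 without the strata, and power with them of 0.813, 0.873 and 0.935.

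**6. The scale of d.** Section 12.0 derives d = 0.90 from cross-sectional groups and raw SDs. For pre/post correlation r, the SD of change is √(2(1 − r)) raw SDs. The two scales agree at r = 0.5. At an assumed r = 0.7 the SD of change is √0.6 = 0.775, so 0.90 raw SD equals 0.90/0.775 = 1.16 SDs of change. Power without and with status is then 0.940 and 0.953, 0.948 and 0.977, and 0.959 and 0.994 at R² of 0.10, 0.25 and 0.40: gains of about 1, 3 and 4 points. At r = 0.8 power is already about 0.99 either way.

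**The case against.** The best reply is that this is one wrong letter. Three strata leave a single open cell, the Background and Aim 2 point to it, and no trained team would misread it. That stands as to intent, and it would be wrong to infer that the trial means to drop patients with an isolated MEP deficit. It does not answer the second part: the exclusion appears in three sections and has no effect once the letter is corrected.

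A reader might rescue the exclusion as a quota for filled strata. The sentence on equal repartition does not support this, because it goes on to speak of the spread between arms, which is balance and not a cap. A reader might also link it to the repeatability aim for the pressure tests, "with the goal of matching the highest 2 trials within 10" cmH2O; but that is given as a goal and is not tied to exclusion.

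It would also go too far to say that the meaning of decreased has no anchor. The Background cites a paper on reference values where it mentions the profiles, the pressure procedures cite one on MIP reference equations, and height and weight are collected for the assessments. A cut-off is not stated, but a source is indicated.

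On the model, it is fair to say that the gain depends on an R² the documents do not give, and that the larger gains assume d is in SDs of change. Both points stand. So does the caution that section 12.0 allows other distributions and a log link, which were not simulated.

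**Conclusion.** The misprint and the empty exclusion are certain from the text and should be fixed, since the protocol calls this list crucial and uses it for both allocation and eligibility.

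The omission from Aim 1 is a missed improvement and not a validity error. A reader might infer that ignoring the strata risks false positives. The calculations show the opposite in the normal, identity-link case: the test is conservative, and only so far as MIP and MEP status predict change. A reader might also take the 9- or 13-point gain as what the trial would get. That needs both a high R² and d read in SDs of change. On the raw scale with r = 0.7 the gain is at most about 4 points over the range examined, and with no stratum effect on change it is essentially none.

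**What to change.** - In section 10.0, change stratum 2 to preserved MIP and decreased MEP, so that the strata form the full two-by-two. This is a one-word correction.
- Reconcile sections 5.0, 9.0 and 10.0: delete the stratification exclusion, or state in one or two sentences exactly whom it removes.
- As a free improvement, add MIP status and MEP status to the Aim 1 analysis, either crossed with time or as covariates in a change-score or baseline-adjusted model. Main effects alone are not enough with an identity link, because a status effect that is constant over time cancels from the pre/post contrast. The cost is about two residual degrees of freedom (42 to 40 with 15 completers per arm).

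No extra patients or visits are needed, and the sample size stays as it is.
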